There will be a total of 4 testing visits (visits 1, 2 3 and 4 as described above) prior to starting the study, after which, subjects will receive treatment for visits 5-16). After completion of treatment, the subjects will then be re-tested on the baseline assessments and resting state MRI (Post-intervention Visits 17, 18, 19 and 20the total amount of visits for TBI subjects will be 20.). Healthy Control Subjects will have a total of three testing visits (1-3) only.

The subjects with TBI will then be randomly assigned to one of two groups, each consisting of 10 subjects. Subjects will be randomized by a simple randomization method. They will have a 50/50 chance of being in either group by flipping of a coin. Randomization will be carried out by the PI. Subjects and study personnel performing assessments and data analysis will be blind to group assignment. Only the PI will be unblinded.

The experimental group will receive active tDCS for 20 minutes and computerized cognitive training twice a week for 30-45 minutes for 6 weeks as described below. The control group will receive sham-tDCS 20 minutes and computerized cognitive training for 30-45 minutes twice a week for 6 weeks (12 training sessions). The sham group will not receive real tDCS after completion of the study.

In addition, we will conduct a qualitative interview with each of the subjects. Giorgi's phenomenology (Giorgi 1985; Kleiman 2004) is the method that will be used to describe the experiences of persons undergoing tDCS for treatment of TBI. In-person audio-taped interviews will be conducted at the completion visit by an experienced qualitative interviewer and immediately transcribed verbatim. Interviews are expected to range from 30 minutes to 1 hour. Each of the subjects will be asked the open-ended question, "Please tell me about your experience undergoing tDCS for the treatment of traumatic brain injury." Probes included the following questions: "What was the experience like for you? What should we continue to do and what should we change to make the experience better for patients?" Themes will be derived using the constant comparative method (Sandelowski 1995; Thorne 2000).

II. CHARACTERSTICS OF THE RESEARCH POPULATION

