3) To determine whether the tDCS intervention produces stronger functional connectivity between fronto-limbic networks compared with sham-tDCS. Hypothesis: Patients receiving tDCS + cognitive re-training will show higher temporal correlation between the frontal and limbic areas compared to baseline than patients receiving sham tDCS + cognitive re-training.

Analyses of the resting state fMRI images will be performed using AFNI and FSL software packages (www.fmrib.ox.ac.uk/fsl/) using standard procedures. The images will be slice-time corrected, despiked, and motion corrected using AFNI, and time series detrending will be performed. The Brain Extraction Tool (Smith 2002; Smith, Jenkinson et al. 2004; Woolrich, Jbabdi et al. 2009) (BET) will be used to skull strip the images, which will be spatially smoothed using a Gaussian kernel. In the first stage analysis, data from each subject will be individually modeled. The stimulus time course will be convolved with a gamma function and the general linear model (GLM) will be employed with motion parameters as covariates. Additionally we will use temporal bandpass filtering (0.01 Hz < f < 0.1Hz), regression of the six motion parameters and of white matter and cerebrospinal fluid signals. Average resting state time series will be obtained for all the seeds of interest, particularly in the **cingulate motor cortex, and dorsolateral premotor cortex** based on prior studies.(Marshall, Zarahn et al. 2009) FSL FEAT will be employed to find the brain voxels that correlate with the seed time series in each subject. Individual functional connectivity maps will be registered to the MNI space and entered into group-level analyses. Higher level analyses will be carried out using FEAT. Connectivity patterns pre- and post-treatment will be compared for all the seeds of interest. Gaussian random field theory will be used for cluster-level multiple comparisons correction (minimum $Z > 2.3$; $p < .05$, corrected) for the resting state analyses.

Data Monitoring: The PI will be overall responsible for data monitoring.

(1) Types of Data or Events: All accumulated outcome data, enrollment numbers, reportable event data (including adverse reactions and unanticipated problems) and overall compliance with the protocol will be monitored.

(2) Responsibilities and roles for gathering, evaluating, and monitoring the data: The PI will be responsible for monitoring the data collected, including data related to adverse events and

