unanticipated problems. Accuracy of data collection from assessments at the Motor Recovery Laboratory will be verified on an ongoing basis and at weekly lab meetings. Compliance with the protocol will be verified by the PI and co-investigators. Independence of judgment will be assured by using independent assessors for outcomes.

(3) Reporting adverse events and unanticipated problems to the monitoring entity: Any adverse reaction to the assessment procedures or intervention procedures, although expected to be minimal, will be reported to and compiled by the PI and Co-PI jointly on an ongoing basis. Reportable events will be reported by the PI to the IRB at NYU Medical Center within 5 business days.

(4) Assessments: Assessments will be performed on a quarterly basis to review and assess all the data or events captured under the Data Monitoring Plan to examine any "unanticipated problems involving risks to participants or others" (i.e., as to whether they are unexpected, related to the research, or harmful).

(5) Criteria for action: If significant research-related and harmful adverse events are found at the quarterly assessments, the study will be terminated.

(6) Procedures for communicating; dissemination of safety information: Outcomes of monitoring entity reviews will be communicated to the IRB at NYU Medical Center annually unless there are reportable adverse events or criteria for action.

3. Data Storage and Confidentiality. Data from assessments at the Motor Recovery Laboratory will be stored securely in the PI's office,, at the Rusk Institute of Rehabilitation Medicine, NYU Medical Center. All data will be labeled by subject codes only, and stored on password-protected computers and/or in locked filing cabinets in the secure offices of the PI. Videotapes of the assessments will be stored on password-protected computers and servers, and backed up on DVDs stored in locked cabinets, in the secure offices of the PI. Videotapes will be stored for at least 3 years following the conclusion of the study, and may be stored indefinitely thereafter. Data collection computers will be in locked, fixed locations (no mobile laptops), password protected, and on local networks. Only the PI and her HIPAA certified delegates will have access to the data.

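### The only unblinded person, the PI, who also randomises, is responsible for monitoring that includes accumulating outcome data, so she can see trends by arm while discretionary decisions are still open

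*Protocol*

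**What the plan says.** Protocol I.3 (Study Design) sets the roles in the randomised part: "Randomization will be carried out by the PI", by coin flip, and "Only the PI will be unblinded". The same section states: "Subjects and study personnel performing assessments and data analysis will be blind to group assignment".

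Protocol III.2 (Data Analysis and Data Monitoring) begins its monitoring plan with "The PI will be overall responsible for data monitoring". Item (1) lists what is monitored, starting with "All accumulated outcome data, enrollment numbers, reportable event data". Item (4) sets a quarterly assessment "to review and assess all the data or events captured under the Data Monitoring Plan"; its declared aim is to find unanticipated problems that put participants or others at risk. Item (5) gives the single criterion for action: the study ends if significant, harmful, research-related adverse events are found. Under item (3), the PI and Co-PI compile adverse reactions jointly, and the PI sends reportable events to the IRB within 5 business days.

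**The concern.** Each provision is ordinary in a small single-site pilot; the difficulty is the combination. The one person who knows every subject's arm is made responsible for looking over outcomes as they accumulate. The protocol does not say that she sees them pooled or masked.

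Meanwhile several decisions rest on judgement: whether an event is related to the research, whether a subject with a difficulty is withdrawn, and whether enrolment goes on. Knowing which arm is ahead can colour such judgements without any intent. That would weaken the active-versus-sham comparison in Aim 2, and III.2 says those results will be used to size later trials.

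**Working it through.** There is no stated figure to reproduce. III.2 calls the sample size small and arbitrary and gives no power calculation. The check is therefore a reading of the sections side by side, plus a head count.

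**Who knows the arm, and who is responsible for the data**

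| Question | Protocol location | Answer |
|---|---|---|
| Who knows the arm? | I.3 | The PI only |
| Who allocates? | I.3 | The PI, by coin flip |
| Who is responsible for monitoring? | III.2 | The PI |
| Does monitoring include outcomes? | III.2 (1) | Yes, all accumulated |
| How often, and how much is reviewed? | III.2 (4) | Quarterly, everything under the plan |
| Is the review pooled or masked? | III.2 | Not stated |
| Who carries out the quarterly review? | III.2 (4) | Passive wording; the PI by inference from overall responsibility |
| Who applies the termination criterion? | III.2 (5) | Not named |

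**Do the stated safeguards separate arm from outcome?**

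- Independent outcome assessors (III.2 (2)) protect the measurement. They do not protect decisions taken by someone who knows the arm.
- Subject codes (III.3) do not mask the PI, because III.4 gives the PI and the study coordinator access to the code.
- Reporting to the IRB is not described as an independent review of outcomes.

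**Does any stated function need outcomes by arm?** The aim in III.2 (4) is risk and the criterion in (5) is adverse events. Neither calls for efficacy data by arm.

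**What is left to judgement?**

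- Relatedness: the word significant in III.2 (5) is undefined.
- Withdrawal: IV (Protection against Risks) covers any adverse event or difficulty, including events unrelated to the study, and names no blinded decision-maker.
- Continued enrolment: I.3 and II.1 plan 40 TBI subjects, while I.3 and III.2 also give 10 per group, that is 2 × 10 = 20.

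**Head count**

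- At 20 randomised: 1/20 = 5%, 2/20 = 10%.
- At 40 randomised: 1/40 = 2.5%, 2/40 = 5%.

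These are shares of the randomised subjects that one or two decisions would touch. They do not estimate bias.

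**Number of informative reviews.** Quarterly means 4 reviews per year. No accrual period is given, and post-treatment outcomes arise only at Visits 17-20, so early reviews would hold few of them. Four per year is a ceiling on informative looks.

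**Other routes to outcomes.** III.1.1 has the PI or her delegates complete the Moss Attention Rating Scale (MARS). V has the PI and delegates administer assessments, deliver tDCS and analyse data. Both conflict with I.3, where those who assess and analyse are blind and the PI is not.

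**The case against.** The fair counter-reading is that monitoring outcome data means checking data quality. III.2 (2) speaks of verifying accuracy of collection, (4) is aimed at unanticipated problems, and nothing provides for tabulating results by arm. That stands as far as it goes: no interim comparison is planned. It does not remove the exposure, because the PI needs no table to connect an outcome with an arm she already knows.

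A reader might infer more in four ways, and the document does not support any of them.

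- *The PI ends the study on results by arm.* The only written criterion is harm, no decision-maker is named, and adverse events are compiled jointly with the Co-PI.
- *The type I error is inflated.* Simulated stopping at the first nominal p < 0.05 gives about 0.084 with two looks and 0.137 with four at 10 per arm. Both that stopping behaviour and the number of looks are assumptions the protocol does not make, so these figures carry no weight here.
- *Allocation follows the outcomes.* A fair coin that is honoured cannot do so. The allocation weakness is that the PI flips the coin with no concealment described, and it exists whether or not she sees outcomes.
- *Removing outcome data from review costs nothing in safety.* Worsening attention, emotion or quality of life in these patients could itself signal harm, so a route for it must remain.

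Two practical objections also stand. Deleting outcome data from the monitoring list does not close the routes in III.1.1 and V. The Co-PI's blindness follows only by default from I.3; III.1.5 has trained personnel deliver stimulation and turn the sham off after 5 seconds, so an operator may know the arm. Pilot status lowers the stakes, but Aim 2 still tests active against sham.

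**Conclusion.** The point holds in a limited form. As written, the unblinded PI, who also randomises, is responsible for monitoring that includes accumulating outcomes, and no stated safeguard keeps trends by arm from her while withdrawal, relatedness and continued enrolment are open to judgement. The conclusion assumes that the PI takes part in the quarterly review, which follows from her overall responsibility but is not stated outright. It concerns access and opportunity; the protocol plans no efficacy stop and no comparison by arm.

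The size of any bias cannot be computed from the document. It is a should-change point: the correction is nearly free and the access serves no stated purpose.

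**What to change.** 1. In III.2, limit the PI's quarterly review to adverse events, unanticipated problems, enrolment and protocol compliance, and take outcome data out of that review.
2. Have blinded staff check outcome data for completeness and accuracy, without arm labels, until the last subject's Visit 20. Any individual worsening they notice goes to the PI as a safety event.
3. Have a team member confirmed to be blind record relatedness before the arm is considered. The Co-PI can do this only if not delivering stimulation.
4. Reconcile III.1.1 (MARS) and V with I.3, so that the unblinded PI neither rates nor analyses outcomes.

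The cost is protocol wording and confirmation of who is blind. If the Co-PI delivers stimulation, another blind team member is needed for step 3. The downside is that the PI loses sight of outcome trends during the trial. These steps do not repair the PI's unconcealed coin flip, which needs its own correction.

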2.4 We will use resting state functional connectivity MRI (fMRI) to directly test the hypothesis that tDCS strengthens fronto-limbic connections involved in emotional processing. Resting state functional connectivity MRI (fMRI) is a recently evolving method from which functional connectivity between distant brain regions is extracted based on low-frequency fluctuations. It allows for the identification of discrete functional networks in the brain. Distributed networks of brains regions have been shown to display temporally correlated patterns of spontaneous activation. This temporal coherence tends to occur in the brain regions that are anatomically connected (Zhang and Raichle 2010). Furthermore, functionally connected networks derived using resting state approaches mirror activation patterns found in task-based functional imaging studies. For clinical purposes, the strength and nature of network connections can be compared in clinical and healthy populations, or resting state can be used in a repeated measures fashion to assess changes within clinical groups. Resting state fMRI had been employed in a small number of studies of TBI patients to examine how network connectivity changes with recovery (Nakamura, Hillary et al. 2009; Hillary, Slocomb et al. 2011).

3. Study Design.

Forty (40) individuals status post TBI with complaints of emotional dysfunction 6 months post-brain injury and twenty-five (25) healthy controls will participate in the study. We expect a

total of 65 subjects to enroll. After obtaining informed consent, they will be screened to ensure that they meet inclusion-exclusion criteria at Visit 1. At visit 1 subjects also will be tested on chemosensory performance evaluation using Sniffin' sticks test and oculomotor movement evaluation using King-Devick test Subjects meeting criteria will then be tested at baseline on neuropsychological assessments, tests of attention (at Visit 2), and the emotional function battery (at Visit 3). The TBI subjects will also undergo resting-state MRI (at Visit 4).

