- 7. Vulnerable Subjects.** Although TBI patients have some cognitive impairment, we will only consent patients who have been determined to have the capacity to give consent. This determination will be made by [name], [name] Im or [name] who are specialists in Brain Injury and will screen patients to determine if they are in a stable cognitive state, whose capacity to give consent is not expected to fluctuate. Only such patients will be enrolled in the study. We will provide information to the subjects in terms that they can fully understand, and capacity to consent will be determined by the subject's verbal understanding of the protocol as determined by the PI. We will not exert any overt or covert coercion, and no financial incentive will be offered. The consent document that each potential subject will be asked to sign will be written in the language that he or she understands, and will be approved by the IRB.

III. METHODS AND PROCEDURES

1. Methods and Procedures.

Patients will sign informed consent and be required to undergo self-assessment (using the TIRR symptom checklist), caregiver assessment (using the Neurobehavioral Functioning Inventory/NFI), and clinician assessment (using NRS-R) to determine neurobehavioral status on study entry. Screening procedures will also include medical history and interview, review of medications and imaging records to ensure that participants meet inclusion/exclusion criteria. Screening procedures will take place at the Motor Recovery Laboratory. The following outcome measures will be administered at baseline and at the end of the 6-week tDCS intervention.

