1.5 Intervention with active and sham tDCS and computerized cognitive re-training

After providing informed consent approved by the IRB of New York University School of Medicine (NYUSoM), all patients will undergo testing with the above listed outcome measures. They will then be randomized into the two intervention groups, the groups being (1) tDCS + cognitive re-training, and (2) sham tDCS + cognitive re-training. The intervention will be carried out for 20 minutes twice a week for 6 weeks during which the subjects in each group will be engaged in re-training using visual cognitive re-training software programs for 30-45 minutes during each session (www.positscience.com). These re-training programs have been used in patients with TBI and have been shown to be effective (Fisk, Novack et al. 2002; Calvanio, Williams et al. 2004; Novack, Banos et al. 2006). Cognitive re-training will thus be individualized to each patient's cognitive level, but still be systematic, and will not need direct one-on-one supervision by a neuropsychologist.

Transcranial direct current stimulation will be delivered by trained study personnel using the saline-soaked pair of surface sponge electrodes (35 cm²) delivered by a specially developed, battery-driven, constant direct current stimulator (Fisher Wallace Cranial Stimulator, Fisher Wallace Laboratories, New York) with a maximum output of 4 mA (**Fig. 1**). FDA approval: The Cranial Stimulator is an FDA cleared device indicated for application of electrical stimulation to a patient's head to treat insomnia, depression, or anxiety. TBI subjects experience insomnia, depression and anxiety and all subjects enrolled in this study will have some combination of these problems. The purpose of this study is to understand the mechanisms behind the depression, anxiety and insomnia that patients with TBI experience. The hypothesis is that emotional dysregulation contributes to the symptoms. This device will therefore be used in alignment with FDA clearance indications. To stimulate the DLPFC, the anode electrode will be placed over F3 according to the 10-20 international system for EEG electrode placement (Fregni, Boggio et al. 2005) (**Fig.2**). The cathode will be placed over the contralateral supraorbital area.

Fig.1. FDA approved Fisher Wallace Cranial Stimulator.

[figure not shown]

Fig.2. Placement of electrodes (Rosa and Lisanby 2012).

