- 2) **Emotional recognition:** Responses to emotion recognition questions, using both the reactivity film clips described above and picture stimuli will be recorded and coded; coded data from patients and controls will be compared.
- 3) **Emotional regulation with disgust videos:** For the three conditions, physiological responses (as described above) will be recorded, and input from baseline will be subtracted from input across the most intense segment of the clip. Facial behavior will be recorded and coded. Data from patients and controls will be compared.

For coding facial behavior, coders will be blind to the diagnostic status of the participant and code videos with sound muted; coding will be assessed for inter-rater reliability

Pearson's correlation analysis will be performed to examine the relationship between reaction time (RT) scores indicating alerting, orienting and executive attention on the ANT-R and emotional recognition, reactivity and regulation scores. Differences in patients and controls will be computed. We will also correlate the clinical scores on the MARS with the ANT-R and the TAS-20 scores with the emotional battery scores. We expect that deficits in selective or executive attention will be related to deficits in emotional appraisal in the patients.

2) To determine whether anodal tDCS applied over the dorsolateral prefrontal cortex in conjunction with computer assisted cognitive re-training of attention will lead to greater improvement in attention and/or emotional regulation compared with sham-tDCS + cognitive re-training. Hypothesis: Patients receiving tDCS + cognitive re-training will show greater improvement in post-intervention measures of attention and emotional regulation.

A 2 (condition) x 2 (pre and post session) repeated measures ANOVA with a priori orthogonal contrasts will be performed on the variables related to executive attention and emotional appraisal to determine whether there is a difference both within and between groups. This analysis will also provide data for power analysis to determine the sample size for subsequent interventional studies. We expect that patients receiving tDCS + cognitive re-training will show greater improvement in post-intervention measures of attention and emotional regulation.

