Protection against Risks. Potential risks and discomfort will be minimized to the greatest extent possible through such procedures as appropriate training of personnel and monitoring of subjects. Subjects may take rest breaks as needed during therapy and assessment sessions so that the risk of fatigue is minimized.

In order to minimize any emotional distress, we will explain to the subjects that they may become upset so that they are forewarned. We will explain that the emotional stimuli are similar to everyday experiences that evoke emotional responses. The examination of emotional reactivity and the treatment included in the study will examine how well they cope with real-life situations that may be upsetting to them. In case of any adverse event or difficulty, including events unrelated to the study that make it difficult to continue with the protocol, the subject will be withdrawn from the study and referred for treatment, counseling, or other necessary follow-up. Physicians ([name] and [name] Im) and a neuropsychologist ([name]) who specializes in treating patients with TBI are included on the team, and will be available to counsel, treat and provide other necessary follow-up in such an event. This study does not provide financial assistance for medical or other injury-related costs.

Risks to confidentiality will be minimized by maintaining a secure, immobile computer database. Subjects will be identified by code rather than by name.

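### A subject withdrawn during treatment leaves the study altogether, so the Aim 2 and Aim 3 arm comparisons have no post-intervention value for that subject

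*Protocol*

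**What the plan says.** **The rule.** Section IV of the Protocol, under Protection against Risks, covers adverse events and difficulties, including "events unrelated to the study that make it difficult to continue with the protocol, the subject will be withdrawn from the study". The consequence in full is that "the subject will be withdrawn from the study and referred for treatment, counseling, or other necessary follow-up", the care coming from the team's physicians and neuropsychologist. What ends is participation in the study; stopping stimulation while staying in assessment is not offered.

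**The schedule.** Section I.3 (Study Design) places treatment at Visits 5-16 and the repeat assessments at Visits 17-20: "After completion of treatment, the subjects will then be re-tested on the baseline assessments and resting state MRI". Section III.1 (Methods and Procedures) gives two outcome time points: "The following outcome measures will be administered at baseline and at the end of the 6-week tDCS intervention".

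**Randomisation.** Section III.1.5 has all patients tested at baseline, and then: "They will then be randomized into the two intervention groups". A subject withdrawn during treatment is thus already randomised and has a baseline value.

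**The analyses.** For Aim 2, section III.2 plans "A 2 (condition) x 2 (pre and post session) repeated measures ANOVA". For Aim 3 it says: "Connectivity patterns pre- and post-treatment will be compared for all the seeds of interest".

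**Sample size.** Section I.3 gives "Forty (40) individuals status post TBI with complaints of emotional dysfunction 6 months post-brain injury", and section II.1 repeats the figure of 40. Sections I.3 and III.2 also state 10 subjects in each randomised group.

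**The concern.** The withdrawal rule and the visit schedule together decide whose outcomes exist. Someone withdrawn at, say, Visit 8 was randomised and measured at baseline but is never due for a second measurement. Both arm comparisons need a pre and a post value, so that subject drops out of them.

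An analysis plan cannot repair this. It can say how missing values are handled, but it cannot supply visits that were never held. The rule on conduct is fixed in the protocol and has to be changed there.

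At stake are some precision and the comparability of the randomised arms. The rule stands in a paragraph about emotional distress, and emotional regulation is an Aim 2 outcome, so those who leave could differ on outcome from those who stay. The pilot data are also meant to size later trials, and completer-only data would feed those estimates.

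**Working it through.** **Step 1: follow one subject through the text.** Baseline at Visits 1-4 (sections I.3, III.1), then randomisation (III.1.5), then treatment from Visit 5. An event during Visits 5-16 makes continuing difficult, and the subject is withdrawn from the study (IV). Re-testing at Visits 17-20 follows completion of treatment (I.3), so this subject has a pre value and no post value. The follow-up named in section IV is clinical care, not outcome collection. Withdrawals before randomisation do not affect the arm comparison and are left out.

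**Step 2: precision.** The plan states no power, effect size, SD or withdrawal rate, so there is no figure of its own to reproduce. The group-by-time interaction in a 2 x 2 pre/post ANOVA is a two-sample comparison of changes. In units of the SD of change,

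SE = sqrt(1/nA + 1/nS),

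with nA and nS the numbers with a post value in the active and sham arms. The starting sizes are 10 per arm (stated) and about 20 per arm (40/2, assuming an even split). The numbers lost are assumptions.

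| Post values lost | SE from 10 per arm | Ratio | SE from 20 per arm | Ratio |
|---|---|---|---|---|
| none | 0.447 | 1 | 0.316 | 1 |
| 1 in one arm | 0.460 | 1.027 | 0.320 | 1.013 |
| 1 in each arm | 0.471 | 1.054 | 0.324 | 1.026 |
| 2 in one arm | 0.474 | 1.061 | 0.325 | 1.027 |
| 2 in each arm | 0.500 | 1.118 | 0.333 | 1.054 |

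Example: sqrt(1/9 + 1/10) = 0.460, and 0.460/0.447 is about 1.03 (1.027 unrounded).

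**Step 3: bias.** Let p be the share lost in an arm and gap the completer mean minus the withdrawn mean. The completer comparison is then off by

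bias = pA x gapA - pS x gapS.

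With an assumed gap of 0.5 to 1 SD:

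- 1 versus 0 lost: 0.05 to 0.10 SD at 10 per arm; 0.025 to 0.05 SD at 20 per arm.
- 2 versus 0 lost: 0.10 to 0.20 SD at 10 per arm; 0.05 to 0.10 SD at 20 per arm.
- 1 versus 1 lost, gaps of 1 and 0: 0.10 SD at 10 per arm; 0.05 SD at 20 per arm.
- 1 versus 1 lost, equal gaps: 0.

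Bias is also zero if withdrawal is unrelated to outcome. Equal numbers lost do not by themselves remove it.

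**Step 4: what retesting could recover.** Not everyone who stops can or will return. If 2 are lost per arm and half are retested, the SE penalty falls from 11.8% to 5.4% at 10 per arm, and from 5.4% to 2.6% at 20 per arm.

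**The case against.** The strongest reply is that the rule protects subjects and that few outcomes are recoverable. On its natural reading, the trigger is an event that makes it hard to go on with the protocol, and the protocol includes the testing. Some of these subjects would be unfit or unwilling to repeat the films, the startle probe and the MRI; section IV.1 itself calls the startle probe potentially distressing. This stands, and it limits how much the fix can gain.

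A reader might infer that any adverse event, even a passing itch under the electrode, removes a subject. The wording can be stretched that far, but the rest of the protocol does not support it. Section III.1.5 says patients will feel itching when stimulation starts and relies on that sensation for blinding, so it can hardly be grounds for withdrawal.

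The phrase in section III.1 about the end of the 6-week intervention can be read by calendar. A subject who merely misses sessions is then not clearly barred from post-testing. That is fair, but it does not help someone actually withdrawn from the study.

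Some text near the consent section was not available, and neither was the consent form. Either could describe withdrawal procedures, so the absence of an early-termination assessment is established only for the text at hand.

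Finally, every loss count and gap above is assumed. Section IV.1 calls non-serious events infrequent, section III.2 (Data Monitoring) expects adverse reactions to be minimal, and the sample size is described as arbitrary for a pilot. No stated power or precision fails.

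**Conclusion.** The point holds as a minor one. For a randomised subject withdrawn during Visits 5-16, the text available provides no post-intervention outcome, and the comparisons for Aims 2 and 3 then rest on completers.

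The loss of precision is probably small: 2.7% (10 per arm) or 1.3% (20 per arm) in the standard error for a single subject lost, and nothing if no one is withdrawn. The actual size cannot be derived from the protocol.

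A reader might go further and infer that the arm comparisons are materially biased, because active subjects receive 20 minutes of current while sham is switched off after 5 seconds. That is a possible route to unequal loss, but the protocol gives no withdrawal rates by arm and no evidence that withdrawn subjects differ on outcome. The bias figures show only what would follow under the stated assumptions.

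**What to change.** In section IV, Protection against Risks, separate stopping the intervention from leaving the study, for example:

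*Subjects who stop the intervention early remain in the study unless they withdraw consent, and are asked, if clinically appropriate, to complete the post-intervention assessments (Visits 17-20), in whole or in part, at the time already scheduled for them at the end of the 6-week period.*

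Fixing the time at the end of the 6 weeks keeps the pre-post interval the same as for completers. Allowing part of the battery lets a subject decline the startle probe or the MRI and still contribute other outcomes.

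The cost is a change to protocol and consent wording, and holding visits that are already planned for a few more subjects. One consequence has to be accepted: some post values will come from subjects with less than full treatment exposure, so the comparison describes assignment to an arm rather than completed treatment. Clinical decisions to stop, referral for care and the right to withdraw fully are unchanged.
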